10.5. List of Abbreviations and Specialist Terms

The following abbreviations and specialist terms are used in this study protocol.

 Table 14:
 List of Abbreviations and Specialist Terms

Abbreviation or Specialist Term	Explanation
μg	Micrograms
AE	Adverse event
ALP	Alkaline phosphatase
ALT	Alanine aminotransferase
ADaM	Analysis Data Model
ANCOVA	Analysis of covariance
AST	aspartate aminotransferase
BCVA	Best-Corrected Visual Acuity
CFR	Code of Federal Regulations
CIOMS	Council for International Organizations of Medical Sciences
СМН	Cochran–Mantel–Haenszel
CONSORT	Consolidated Standards of Reporting Trials
CRF	Case Report Form (paper or electronic)
CRO	Contract Research Organization
CST	Central subfield thickness
DMC	Data Monitoring Committee
eCRF	Electronic Case Report Form
EDC	Electronic Data Capture
ESI	Event of Special Interest
ETDRS	Early Treatment Diabetic Retinopathy Study
FA	Fluorescein angiography
FAS	Full analysis set
FDA	Food and Drug Administration
FP	Fundus photography
GCP	Good Clinical Practice
GEE	General estimating equation
GGT	Gamma glutamyl transferase
hCG	Human chorionic gonadotropin
НСТ	Hematocrit

Abbreviation or Specialist Term	Explanation
HDL	High-density lipoproteins
HGB	Hemoglobin
HIPAA	Health Insurance Portability and Accountability Act
ICF	Informed Consent Form
ICH	International Council for Harmonisation
IEC	Independent Ethics Committee
IOP	Intraocular Pressure
IP	Investigational Product
IRB	Institutional Review Board
IWRS	Interactive Web Response System
LDH	Lactate dehydrogenase
LDL	Low-density lipoproteins
LOCF	Last Observation Carried Forward
МСН	Mean corpuscular hemoglobin
МСНС	Mean corpuscular hemoglobin concentration
MCV	Mean corpuscular volume
mL	Milliliters
MMRM	Mixed-effects model for repeated measures
mTOR	Mammalian target of rapamycin
NIU-PS	Non-infectious uveitis of the posterior segment of the eye
NPDR	Non-proliferative diabetic retinopathy
OCT	Optical coherence tomography
PDR	Proliferative diabetic retinopathy
PGx	Pharmacogenomic
PLT	Platelets
РР	Per-protocol
PVU	Pharmacovigilance Unit
RBC	Red blood cell
SAE	Serious adverse event
SAP	Statistical Analysis Plan
SoA	Schedule of Activities

 Table 14:
 List of Abbreviations and Specialist Terms (Continued)

Abbreviation or Specialist Term	Explanation
SOC	System Organ Class
SDTM	Study Data Tabulation Model
SUN	Standardization of Uveitis Nomenclature
SUSAR	Suspected Unexpected Serious Adverse Reaction
VA	Visual Acuity
VFQ-25	Visual Functioning Questionnaire
VH	Vitreous haze
WBC	White blood cell

 Table 14:
 List of Abbreviations and Specialist Terms (Continued)

12. APPENDICES

12.1. Appendix 1: National Eye Institute Visual Functioning Questionnaire – 25 (VFQ-25)

National Eye Institute Visual Functioning Questionnaire - 25 (VFQ-25) version 2000 (Interviewer Administered Format) plus appendix is provided below.

PB/IA

National Eye Institute Visual Functioning Questionnaire - 25 (VFQ-25)

version 2000

(INTERVIEWER ADMINISTERED FORMAT)

January 2000

RAND hereby grants permission to use the "National Eye Institute Visual Functioning Questionnaire 25 (VFQ-25) July 1996, in accordance with the following conditions which shall be assumed by all to have been agreed to as a consequence of accepting and using this document:

1. Changes to the NEI VFQ-25 - July 1996 may be made without the written permission of RAND. However, all such changes shall be clearly identified as having been made by the recipient.

2. The user of this NEI VFQ-25 - July 1996 accepts full responsibility, and agrees to hold RAND harmless, for the accuracy of any translations of the NEI VFQ-25 Test Version - July 1996 into another language and for any errors, omissions, misinterpretations, or consequences thereof.

3. The user of this NEI VFQ-25 - July 1996 accepts full responsibility, and agrees to hold RAND harmless, for any consequences resulting from the use of the NEI VFQ-25.

4. The user of the NEI VFQ-25 - July 1996 will provide a credit line when printing and distributing this document or in publications of results or analyses based on this instrument acknowledging that it was developed at RAND under the sponsorship of the National Eye Institute.

5. No further written permission is needed for use of this NEI VFQ-25 - July 1996.

7/29/96

-1-

version 2000

Instructions:

I'm going to read you some statements about problems which involve your vision or feelings that you have about your vision condition. After each question I will read you a list of possible answers. Please choose the response that best describes your situation.

Please answer all the questions as if you were wearing your glasses or contact lenses (if any).

Please take as much time as you need to answer each question. All your answers are confidential. In order for this survey to improve our knowledge about vision problems and how they affect your quality of life, your answers must be as accurate as possible. Remember, if you wear glasses or contact lenses for a particular activity, please answer all of the following questions as though you were wearing them.

- 2 -

version 2000

Visual Functioning Questionnaire - 25

PART 1 - GENERAL HEALTH AND VISION

1. In general, would you say your overall health is*:

(Circle One)

READ CATEGORIES:	Excellent 1	
	Very Good 2	
	Good 3	
	Fair 4	
	Poor 5	

2. At the present time, would you say your eyesight using both eyes (with glasses or contact lenses, if you wear them) is excellent, good, fair, poor, or very poor or are you completely blind?

(Circle One)

READ CATEGORIES:	Excellent	1
	Good	2
	Fair	3
	Poor	4
	Very Poor	5
	Completely Blind	6

^{*} Skip Question 1 when the VFQ-25 is administered at the same time as the SF-36 or RAND 36-Item Health Survey 1.0

- 3 -

version 2000

3. How much of the time do you worry about your eyesight?		
		(Circle One)

READ CATEGORIES:	None of the time	1
	A little of the time	2
	Some of the time	3
	Most of the time	4
	All of the time?	5

4. How much pain or discomfort have you had in and around your eyes (for example, burning, itching, or aching)? Would you say it is:

	(Circle (One)
READ CATEGORIES:	None	1
	Mild	2
	Moderate	3
	Severe, or	4
	Very severe?	5

PART 2 - DIFFICULTY WITH ACTIVITIES

The next questions are about how much difficulty, if any, you have doing certain activities wearing your glasses or contact lenses if you use them for that activity.

5. How much difficulty do you have reading ordinary print in newspapers? Would you say you have: (READ CATEGORIES AS NEEDED)

(Circ	le One)
No difficulty at all	1
A little difficulty	2
Moderate difficulty	3
Extreme difficulty	4
Stopped doing this because of your eyesight	5
Stopped doing this for other reasons or not interested in doing this	. 6

6. How much difficulty do you have doing work or hobbies that require you to see well up close, such as cooking, sewing, fixing things around the house, or using hand tools? Would you say: (READ CATEGORIES AS NEEDED)

(Circle One)

No difficulty at all	1
A little difficulty	2
Moderate difficulty	3
Extreme difficulty	4
Stopped doing this because of your eyesight	5
Stopped doing this for other reasons or not interested in doing this	. 6

7. Because of your eyesight, how much difficulty do you have finding something on a crowded shelf?

(READ CATEGORIES AS NEEDED)

CATEGORIES AS NEEDED)	
(Circ	le One)
No difficulty at all	1
A little difficulty	2
Moderate difficulty	3
Extreme difficulty	4
Stopped doing this because of your eyesight	5
Stopped doing this for other reasons or not interested in doing this	. 6
5	

 How much difficulty do you have reading street signs or the names of stores? (READ CATEGORIES AS NEEDED)

(Circ	le One)
No difficulty at all	1
A little difficulty	2
Moderate difficulty	3
Extreme difficulty	4
Stopped doing this because of your eyesight	5
Stopped doing this for other reasons or not interested in doing this	. 6

9. Because of your eyesight, how much difficulty do you have going down steps, stairs, or curbs in dim light or at night? (READ CATEGORIES AS NEEDED)

(Circl	e One)
No difficulty at all	1
A little difficulty	2
Moderate difficulty	3
Extreme difficulty	4
Stopped doing this because of your eyesight	5
Stopped doing this for other reasons or not interested in doing this	6

10. Because of your eyesight, how much difficulty do you have noticing objects off to the side while you are walking along? (READ CATEGORIES AS NEEDED)

(Circl	e One)
No difficulty at all	1
A little difficulty	2
Moderate difficulty	3
Extreme difficulty	4
Stopped doing this because of your eyesight	5
Stopped doing this for other reasons or not interested in doing this	6

11. Because of your eyesight, how much difficulty do you have seeing how people react to things you say? (READ CATEGORIES AS NEEDED)

CATEGORIES AS NEEDED)	
(Circl	le One)
No difficulty at all	1
A little difficulty	2
Moderate difficulty	3
Extreme difficulty	4
Stopped doing this because of your eyesight	5
Stopped doing this for other reasons or not interested in doing this	6

12. Because of your eyesight, how much difficulty do you have picking out and matching your own clothes? (READ CATEGORIES AS NEEDED)

· ·			
	(Circ	le	One)
	No difficulty at all	1	
	A little difficulty	2	
	Moderate difficulty	3	
	Extreme difficulty	4	
	Stopped doing this because of your eyesight	5	
	Stopped doing this for other reasons or not		
	interested in doing this	6	

13. Because of your eyesight, how much difficulty do you have visiting with people in their homes, at parties, or in restaurants? (READ CATEGORIES AS NEEDED)

, (Circl	e One)
No difficulty at all	1
A little difficulty	2
Moderate difficulty	3
Extreme difficulty	4
Stopped doing this because of your eyesight	5
Stopped doing this for other reasons or not interested in doing this	6

14. Because of your eyesight, how much difficulty do you have going out to see movies, plays, or sports events? (READ CATEGORIES AS NEEDED)

(Circle One)

No difficulty at all	1
A little difficulty	2
Moderate difficulty	3
Extreme difficulty	4
Stopped doing this because of your eyesight	5
Stopped doing this for other reasons or not interested in doing this	6

- 7 - version 2000

15. Now, I'd like to ask about driving a car. Are you currently driving, at least once in a while?

(Circle One)

Yes 1 Skip To Q 15c

No..... 2

15a. IF NO, ASK: Have you never driven a car or have you given up driving?

(Circle One)

Never drove 1 Skip To Part 3, Q 17

Gave up..... 2

15b. IF GAVE UP DRIVING: Was that mainly because of your evesight, mainly for some other reason, or because of both your evesight and other reasons?

(Circle One)

Mainly eyesight	1	Skip To Part 3, Q 17
Mainly other reasons	2	Skip To Part 3, Q 17
Both eyesight and other reasons	3	Skip To Part 3, Q 17

15c. IF CURRENTLY DRIVING: How much difficulty do you have driving during the daytime in familiar places? Would you say you have:

(Circle On	ie)
No difficulty at all	1
A little difficulty	2
Moderate difficulty	3
Extreme difficulty	4

- 8 -

version 2000

16. How much difficulty do you have driving at night? Would you say you have: (READ CATEGORIES AS NEEDED)

(Circle One)

No difficulty at all	1
A little difficulty	2
Moderate difficulty	3
Extreme difficulty	4
Have you stopped doing this because of your eyesight	5
Have you stopped doing this for other reasons or are you not interested in doing this	6

16a. How much difficulty do you have driving in difficult conditions, such as in bad weather, during rush hour, on the freeway, or in city traffic? Would you say you have: (READ CATEGORIES AS NEEDED)

(Circle One)

(011010 0	2110)
No difficulty at all	1
A little difficulty	2
Moderate difficulty	3
Extreme difficulty	4
Have you stopped doing this because of your eyesight	5
Have you stopped doing this for other reasons or are you not interested in doing this	6
-	

- 9 -

version 2000

PART 3: RESPONSES TO VISION PROBLEMS

The next questions are about how things you do may be affected by your vision. For each one, I'd like you to tell me if this is true for you all, most, some, a little, or none of the time.

	(Circle One On Each Lin							
READ CATEGORIES:	All of	Most of	Some	A little	None of			
	the time	the time	of the	of the	the time			
			time	time				
17. Do you accomplish less	1	2	3	4	5			
than you would like								
because of your vision?								
,								
18. Are you limited in how								
long you can work or do								
other activities because of	1	2	3	4	5			
your vision?	-	_	-	-	-			
,								
19. How much does pain or								
discomfort in or around								
your eyes, for example,								
burning, itching, or								
aching, keep you from								
doing what you'd like to								
be doing? Would you say:	1	2	3	4	5			
se donig: Hould you say.		-	•	-	•			

- 10 -

version 2000

For each of the following statements, please tell me if it is definitely true, mostly true, mostly false, or definitely false for you or you are not sure.

(Circle One On Each Line)

		Definitely True	Mostly True	Not Sure	Mostly False	Definitely False
20.	l stay home most of the tin because of my eyesight		2	3	4	5
21.	l feel frustrated a lot of the time because of my eyesight		2	3	4	5
22.	I have much less control over what I do, because o my eyesight		2	3	4	5
23.	Because of my eyesight, I have to rely too much on what other people tell me.		2	3	4	5
24.	l need a lot of help from others because of my eyesight	1	2	3	4	5
25.	l worry about doing things that will embarrass mysel or others , because of my eyesight	f	2	3	4	5

That's the end of the interview. Thank you very much for your time and your help.

- 11 -

version 2000

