2.3.3. Secondary Efficacy Endpoints

The secondary endpoints to be assessed for the Double-Masked analysis period include:

- VH 0 or 2-unit response at Month 5: having a VH score of 0 or a decrease (improvement) of at least 2 units (i.e., 2+ to 0, 3+ to 1+, or 4+ to 2+) from baseline in VH score at Month 5 (modified SUN scale)
- VH 0 or 2-unit response at Month 3: having a VH score of 0 or a decrease (improvement) of at least 2 units from baseline in VH score at Month 3 (modified SUN scale)
- VH 0 or 0.5+ response at Month 5: having a VH score of 0 or 0.5+ at Month 5 (modified SUN scale)
- VH 0 or 0.5+ response at Month 3: having a VH score of 0 or 0.5+ at Month 3 (modified SUN scale)
- Change from baseline in VH score at post-baseline visits up to Month 6
- Corticosteroid tapering success with resolution at Month 5 (for the Intent-to-Taper population as defined in Section 6.4): having a prednisone-equivalent oral dose of

0 mg/day and a VH score of 0 at Month 5 without taking any rescue therapies that could affect VH score

- Corticosteroid tapering success with resolution at Month 3 (for the Intent-to-Taper population as defined in Section 6.4): having a prednisone-equivalent oral dose of 0 mg/day and a VH score of 0 at Month 3 without taking any rescue therapies that could affect VH score
- BCVA (Best-Corrected Visual Acuity) 3-line response at Month 5 (for the Vision 20/40 or Worse population as defined in Section 6.6): having an increase (improvement) of at least 3 lines (15 ETDRS letters) from baseline in BCVA
- Change from baseline in BCVA at post-baseline visits up to Month 6
- Central subfield thickness (CST) 50-micron response at Month 5 (for the Macular Edema population as defined in Section 6.5): having a decrease (improvement) of at least 50 microns from baseline in CST at Month 5
- Change from baseline in central subfield thickness (CST) at Month 5 as measured by optical coherence tomography (OCT)
- Change from baseline in CST at Month 3 as measured by OCT
- Change from baseline in the National Eye Institute (NEI) Visual Functioning Questionnaire-25 (VFQ-25) composite score at Month 5
- Use of rescue therapy before Month 5
- Use of rescue therapy before Month 3

Secondary endpoints assessing long-term efficacy will include the following:

- VH 0 response at each visit after Month 6
- VH 0 or 2-unit response at each visit after Month 6
- VH 0 or 0.5+ response at each visit after Month 6

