8.1.5. Efficacy Measures

Table 2 lists all the efficacy measures that were evaluated in LUMINA study.

Efficacy measure	Note
Vitreous haze (VH)	VH was graded using the modified SUN scale as 0, 0.5+, 1+, 1.5+, 2+, 3+, or 4+. A decrease in VH score indicates improvement in the vitreous inflammation.
Overall prednisone-equivalent dose	The overall prednisone-equivalent dose (mg/day) of all eligible systemic corticosteroids in each day
Best-corrected visual acuity (BCVA)	BCVA measures the acuteness or clearness of best- corrected vision, with a range of [0, 110] in ETDRS letters. An increase in BCVA indicates improvement in the best-corrected vision. A 5-letter difference in visual acuity is equivalent to one Snellen line. A BCVA score of 85 ETDRS letters is equivalent to 20/20 vision, which is considered normal vision.
Central Subfield Thickness (CST)	For each eye, the CST was measured using Optical Coherence Tomography (OCT). OCT was performed using reading center certified photographers, equipment, and standardized protocols.
NEI VFQ-25: Composite score and 12 subscales (General Health, General Vision, Ocular Pain, Near Activities, Distance Activities, Vision-Specific Social Functioning, Vision-Specific Mental Health, Vision- Specific Role Difficulties, Vision-Specific Dependency, Driving, Color Vision, Peripheral Vision)	As shown in Appendix A, each NEI VFQ item was recorded to a 0-100 scale. The composite score and subscales will be derived based on the recorded items. An increase in the NEI VFQ-25 composite score or subscale indicates improvement in certain visual function. Note that the 39-item NEI VFQ (VFQ-25 + optional items) conducted at the US sites will be used to derive the VFQ-25 composite score and subscales (double- check).

Table 2:Efficacy Measures

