APPENDIX A. VFQ-25 COMPOSITE SCORE AND SUBSCALES

Following steps will be taken to derive the VFQ-25 composite score and subscales:

Step One: Recode Item Scores

Item Numbers on VFQ-25	Original Response ^a	Recode Value
1, 3, 4	1	100
	2	75
	3	50
	4	25
	5	0
2	1	100
	2	80
	3	60
	4	40
	5	20
	6	0
5, 6, 7, 8, 9, 10, 11, 12, 13, 14, 16, 16a, A3 ^b , A4 ^b , A5 ^b , A6 ^b ,	1	100
$A7^{b}, A8^{b}, A9^{b}$	2	75
	3	50
	4	25
	5	0
	6	*c
15c ^d	1	100
	2	75
	3	50
	4	25
		0
17, 18, 19, 20, 21, 22, 23, 24, 25, A11a ^b , A11b ^b , A12 ^b , A13 ^b	1	0
	2	25
	3	50
	4	75
	5	100
A1 ^b , A2 ^b	0	0
	to	to
	10	100

^a Original response choices as printed in the questionnaire

^b The letter "A" before the item number indicates that this item is an optional item from the Appendix of VFQ-25 questionnaire.

^c A response of '6' indicates that the person does not perform the activity because of non-vision related problems. If '6' is selected, the item will be recoded as missing.

^d Item 15c has 4 levels (1, 2, 3, or 4), but it is recoded to 5 levels by incorporating the response choice for Item 15b: if 15b = 1 then 15c is recoded to 0;

if 15b = 2 or 3 then 15c is recorded to missing.

Score or Subscale	Items to be averaged (after step 1)
General Health	1, A1
General Vision	2, A2
Ocular Pain	4, 19
Near Activities	5, 6, 7, A3, A4, A5
Distance Activities	8, 9, 14, A6, A7, A8
Vision Specific Social Functioning	11, 13, A9
Vision Specific Mental Health	3, 21, 22, 25, A12
Vision Specific Role Difficulties	17, 18, A11a, A11b
Vision Specific Dependency	20, 23, 24, A13
Driving	15c, 16, 16a
Color Vision	12
Peripheral Vision	10
Composite Score	All items except Item 1 and A1

Step Two: Identify Items Needed to Derive VFQ-25 Composite Score and Subscales

Step Three: Derive VFQ-25 Composite Score and Subscales

Score = Sum of all items with a non-missing answer / Total number of items with a non-missing answer, with a range of [0, 100] (0 = Worst possible score; 100 = Best score)

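### VFQ-25 composite: SAP Appendix A restores only item 15c for subjects who give up driving because of eyesight, so the score can rise, or fall too little, when driving is lost

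*Protocol*

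**What the plan says.** Item 15b in Protocol Appendix 1 asks subjects who gave up driving for the reason: mainly eyesight (1), mainly other reasons (2), or both (3). All three answers carry the instruction "Skip To Part 3, Q 17", so none of these subjects is asked 15c, 16 or 16a.

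SAP Appendix A then scores the questionnaire as follows.

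- Step One, footnote d: "if 15b = 1 then 15c is recoded to 0", and "if 15b = 2 or 3 then 15c is recorded to missing". There is no corresponding rule for 16 or 16a.
- Step One, main table: response 5 on items 16 and 16a, worded "Have you stopped doing this because of your eyesight" in the questionnaire, is recoded to 0.
- Step Two: the composite uses "All items except Item 1 and A1".
- Step Three: "Score = Sum of all items with a non-missing answer / Total number of items with a non-missing answer".

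SAP 8.1.5 gives the direction: "An increase in the NEI VFQ-25 composite score or subscale indicates improvement in certain visual function". SAP 2.3.3 lists change from baseline in the "Visual Functioning Questionnaire-25 (VFQ-25) composite score at Month 5" as a secondary endpoint. SAP 8.2.4.2 analyses it by ANCOVA and reports a least-squares mean difference with a 95% confidence interval.

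**The concern.** Take a subject who still drives by day but has stopped night driving and driving in difficult conditions because of eyesight. That subject scores 0 on 16 and 16a, and both zeros count. If the same subject then stops driving altogether because of eyesight, 15c becomes 0 but the other two zeros leave both numerator and denominator. The worse state can therefore get the higher composite. The error also runs the other way, when a subject resumes driving with difficulty.

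The SAP also disagrees with itself here. For the same subject the Driving subscale goes to 0, because 15c is its only non-missing item, while the composite can go up. At stake is the size, and for some subjects the sign, of the change on a listed secondary endpoint. The error arises when vision alters the ability to drive, which is something the questionnaire is meant to capture.

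**Working it through.** The plan states no figure for this scoring, so there is none to reproduce.

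**Inputs from SAP Appendix A, Step Two.** Items per vision subscale, in the order listed: 2 + 2 + 6 + 6 + 3 + 5 + 4 + 4 + 3 + 1 + 1 = 37. Three are driving items, so 34 are not.

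**Assumption.** The other 34 items have mean m and do not change when driving status changes. The documents give no value for m; 70 is used for illustration.

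**Formulas.** D is the sum of 15c, 16 and 16a while the subject drives.

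- Driving: (34m + D)/37
- Gave up, 15b = 1, Appendix A as written: 34m/35
- Gave up, 15b = 1, with 16 and 16a also set to 0: 34m/37

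**When the score rises.** 34m/35 > (34m + D)/37 is equivalent to 35D < 68m, so D < 1.943m. The mean driving item must be below 0.648m.

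**Examples at m = 70 (34 × 70 = 2380).**

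| 15c/16/16a while driving | Driving | Gave up, as written | Change | Gave up, 16 and 16a = 0 | Change |
|---|---|---|---|---|---|
| 50/0/0 | 2430/37 = 65.68 | 2380/35 = 68.00 | +2.32 | 2380/37 = 64.32 | −1.35 |
| 25/25/25 | 2455/37 = 66.35 | 68.00 | +1.65 | 64.32 | −2.03 |
| 100/100/100 | 2680/37 = 72.43 | 68.00 | −4.43 | 64.32 | −8.11 |

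The as-written score after giving up exceeds the repaired one by 68.00 − 64.32 = 3.68 points, whatever the driving answers were before. A subject who resumes driving shows the same changes with the signs reversed.

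**Shorter form.** SAP 8.1.5 ties the 39-item form to US sites and carries an unresolved note to check this. Protocol 8.1.23 has the appendix questions administered without naming a region. Without the optional items there are 22 non-driving items and 3 driving items. The score then rises when D < 44m/23 = 1.913m, a mean driving item below 0.638m. At m = 60 with 25/25/25, the short form goes from (1320 + 75)/25 = 55.80 to 1320/23 = 57.39 (+1.59). The long form goes from (2040 + 75)/37 = 57.16 to 2040/35 = 58.29 (+1.12).

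**15b = 3.** All three driving items are missing, so the composite equals m and rises whenever the mean driving item is below m. At m = 70, 25/25/25 goes from 66.35 to 70.00 (+3.65), and 100/100/100 from 72.43 to 70.00 (−2.43).

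**15b = 2.** All three items are again missing, but for a reason unrelated to vision. This agrees with footnote c, which treats response 6 (does not do the activity for non-vision reasons) as missing.

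**The case against.** The strongest reply is that the defect is narrow and the endpoint minor. VFQ-25 change is not among the secondary endpoints named in Protocol Section 3; the SAP adds it. It is outside the hierarchy in SAP 5.4, and Protocol 9.5.2 plans no formal testing of the other secondary endpoints. The subscales are analysed beside the composite, so a reader will see Driving at 0. All of this stands and limits the weight of the point.

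The reversals also hold the other items fixed. At m = 70, a subject who resumes driving at 25/25/25 loses 1.65 points only if nothing else moves. A rise in the other items from 70 to about 71.8 cancels it: (34 × 71.8 + 75)/37 = 68.0. For 50/0/0 the offset is about 2.5 points: (34 × 72.5 + 50)/37 = 68.0. A subject whose sight recovers enough to drive may well improve elsewhere. That can hide the wrong sign, but the score is still off by the same mechanism.

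A reader might infer that every subject whose driving status changes is misscored. The documents do not support that: for 15b = 2, missing is consistent with the SAP's treatment of non-vision reasons. A reader might also infer a bias in the treatment comparison. None is shown, because the frequency of changes is not given and changes in both arms and both directions partly cancel.

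**Conclusion.** The point holds for 15b = 1. Followed exactly, Appendix A gives a change of the wrong sign when the mean driving item is below about 0.65 of the mean of the other items, and one that is too small otherwise, with other answers unchanged. At m = 70 the discrepancy is 3.68 points for each subject who changes status. The skip instruction itself is not at fault; the omission is in the SAP scoring.

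For 15b = 3 the composite drops all three items although eyesight contributed. Whether missing is intended there is for the sponsor to confirm or revise.

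The effect on the between-arm difference is probably small. As an illustration only, suppose the arms differed by a net 5% to 10% of subjects changing status in one direction. The difference would then be off by 3.68 × 0.05 = 0.18 to 3.68 × 0.10 = 0.37 points. Both that share and m are assumptions. With no formal test on this endpoint, this is a scoring correction that should be made; it does not touch the trial's main conclusions.

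**What to change.** In SAP Appendix A, Step One, footnote d, add that when 15b = 1 items 16 and 16a are recoded to 0 together with 15c. This is the value the SAP already gives response 5 on those items. With other answers unchanged, giving up driving mainly for eyesight then always lowers the composite. In the same footnote, state and justify the rule for 15b = 3. Settle the open note in SAP 8.1.5 on which form is scored.

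The cost is a line of text and a small change to the derivation code, with no new data, since 15b is already collected. It should be done before unmasking.

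Averaging the 11 vision subscales would also remove the reversal for 15b = 1, but it reweights every item. Color Vision and Peripheral Vision, one item each, would go from 1/37 to 1/11. That redefines the endpoint to repair one skip, so the recode is the proportionate choice.
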